8.1.4 MIRV

MIRV (6 mg/kg AIBW) will be administered IV on Day 1 of each 21-day cycle for the combination regimen (SL-172154 + MIRV). The dose of MIRV administered will be based on the subject's AIBW. The weight used for calculation will be obtained before MIRV administration on C1D1 (-14 days). Dosing may be modified per institutional standard of care for changes in body weight on subsequent cycles. Dosing will be modified for significant ($\geq 10\%$) changes in body weight (not influenced by weight gain or loss attributed to fluid retention).

Total number of doses received and infusion outcome (number of infusions completed and interrupted, and number of infusions not completed) will be summarized. MIRV administration for individual subjects will be provided in a data listing by cohort (escalation and expansion), dose level, and date of first dose.

8.2 Maximum Tolerated Dose Evaluation

The MTD evaluation will be based on the DLT Evaluable Population. The number and percentage of subjects with DLT will be presented by dose level for the dose escalation cohorts. The MTD level will be indicated in the summary.

The MTD will be estimated using isotonic regression (based on the DLTs observed in the DLT evaluable subjects). A MAD will be reported if the DLT rate never reaches $\geq 25\%$. Otherwise, an MTD will be reported. Isotonic regression is a way to estimate the MTD under the assumption that toxicity increases with dose. When using isotonic regression, the first step is to identify the doses where the dose-toxicity monotonicity assumption is violated. The DLT estimate is then adjusted for the violators such that the final estimate of the DLT rate increase with the dose. The target DLT rate is then used to select the MTD. For example, suppose that when the trial is completed, the observed DLT rates [<# subjects who experienced DLT]/[# evaluable subjects] at four dose levels are (0/3, 1/3, 0/3, 4/15). In this example the observed DLT rate at Dose Level 2 (i.e., 1/3=33%) is higher than the observed DLT rate at Dose Level 3 (i.e., 0/3=0%). To adjust for this violation, the DLT estimates are replaced with their average, i.e., $(1/3+0/3)/2=1/6$, resulting in the isotonic regression DLT estimates $(0/3, 1/6, 1/6, 4/15) = (0\%, 16.7\%, 16.7\%, 26.7\%)$, which monotonically increases with the dose level. Based on this isotonic estimate, assuming that the trial goal is to find the dose with the DLT rate of 30%, Dose Level 4 will be selected as the MTD. If there are no violators of the dose-toxicity monotonicity assumption, isotonic regression directly uses the observed DLT rates as the final estimates for MTD selection.

In the case of dose levels with estimated toxicity of equal distance (tied dose levels) from the target toxicity of 30%, the following approach will be used: among all tied dose levels the highest dose level with target toxicity $\leq 30\%$ will be selected, unless all tied dose levels have estimated toxicity $> 30\%$, in which case the lowest dose level will be selected.

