9.1.4 Sample Size Determination

The planned sample size is approximately 102 subjects, depending on the number of dose levels evaluated in dose escalation for each of the combinations. Approximately 24 subjects will be enrolled in dose escalation cohorts (12 subjects in PLD cohorts and 12 subjects in MIRV cohorts) and approximately 78 subjects will be enrolled in a dose expansion cohort (an additional 14 subjects at the selected dose in PLD cohort and an additional 64 subjects at the selected dose in MIRV cohort).

All subjects with tumors that are FR α -positive (PS2+ \geq 25%) enrolled in the MIRV combination cohort will be retrospectively binned in expression subgroups (high, medium, low) for study analysis. The goal is to enroll approximately 20 subjects at the potential RP2D in either dose expansion or dose escalation for each of the following three tumor FR α expression subgroups: high (PS2+ \geq 75%), medium (PS2+ \geq 50% and $<$ 75%), and low (PS2+ \geq 25% and $<$ 50%). This estimation is based on the anticipated frequency of subjects with high grade serous ovarian cancer who fall into each of these FR α expression subgroups. If this distribution is not achieved in any subgroup, approximately 10 additional subjects may be enrolled in this dose expansion cohort in order to achieve it.

NOTE: The planned sample sizes may be revised if additional dose levels are evaluated or if more subjects (i.e., subjects available for dosing beyond the number required in a cohort) are enrolled than anticipated. The actual number of subjects to be enrolled for each combination dose escalation will depend upon the number of dose levels evaluated and the number of DLT observed for each dose level and related dose escalation/stay/de-escalation decisions. The Sponsor, in consultation with the SMC, may also elect to add subjects to the dose escalation cohorts if additional data is needed to select the dose level for the dose expansion cohort.

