9.2.4 Safety Analyses

The safety evaluation for each combination regimen will be based on the All-Treated Population and the DLT evaluation will be based on the DLT-evaluable population.

DLTs will be summarized by dose level/regimen for combination dose escalation cohorts. Frequency tables by dose levels will be used to describe safety and tolerability parameters such as: AEs, SAEs, fatal AEs and AEs leading to discontinuation of SL-172154, PLD or MIRV. Changes in toxicity grade for safety assessments (e.g., laboratory parameters, etc.) will also be summarized. Figures may also be presented where appropriate. AEs will be mapped to a Medical Dictionary for Regulatory Activities (MedDRA) preferred term and system organ classification. Concomitant medications will be coded using the World Health Organization Drug Dictionary. All toxicities except CRS and ocular AEs will be graded according to the NCI CTCAE v5.0. CRS will be graded per the ASTCT Consensus Grading Criteria for CRS (described in

Section 3.7.1.2); ocular AEs for the MIRV cohort will be graded per the tables provided in Appendix Section 16.6.

Maximum Tolerated Dose:

The MTD will be estimated using isotonic regression (based on the DLTs observed in DLT-evaluable subjects). Specifically, the MTD is the dose for which the isotonic estimate of the DLT rate is closest to the target DLT rate of 30% among all dose with the isotonic estimate of DLT rate $\geq 25\%$. If two or more doses tie for the smallest difference, the following rules will be performed:

- If the estimated DLT rate $< 30\%$ for all doses, then select the higher dose among the tied doses;
- If the estimated DLT rate for the tied doses are a combination of $< 30\%$ and $> 30\%$ for all doses, then select the higher dose among the tied doses;
- If the estimated DLT rate $> 30\%$ for all doses, then select the lower dose among the tied doses;

A Maximum Administered Dose (MAD) will be reported if the isotonic estimate of DLT rate is less than 25% for all dose levels. Otherwise, an MTD will be reported.

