3.2 Statistical Design

3.2.1 Dose Escalation

The SL-172154 dose escalation will utilize a modified Toxicity Probability Interval-2 (mTPI-2) design [Guo, 2017] with target DLT rate of 30% for the MTD. The mTPI-2 design employs a simple Beta-Binomial Bayesian model with decision rules based on the unit probability mass from the posterior probability of DLT rate. With the target DLT rate of 30%, the posterior probability of DLT rate unit interval (0, 1) is divided into subintervals with equal length of 0.1 that correspond to different dose escalation decisions: subinterval of (0.25, 0.35) is to stay at the current dose, subinterval below 0.25 is to escalate to next higher dose, and subinterval above 0.35 is to de-escalate to the next lower dose. Subjects will be enrolled in cohorts of approximately 3 subjects during the dose escalation. After each cohort of approximately 3 subjects, the posterior unit probability for subintervals will be calculated based on a noninformative prior distribution for the DLT rate (Beta (1,1)) and the total number of subjects with DLTs and DLT evaluable subjects for the current dose. A dose escalation/stay/de-escalation decision that corresponds to the subinterval with the highest unit probability mass will be selected. A minimum of 3 DLT evaluable subjects will be enrolled to a dose level and evaluated for DLT before a dose escalation/stay/de-escalation decision can be made unless unacceptable toxicity is observed prior to the enrollment of 3 subjects e.g., two subjects experience DLT before the third subject enrolls. A dose level will be considered unsafe, with unacceptable toxicity and no additional subjects enrolled at that dose level and above, if it has an estimated 95% or more probability of exceeding the target DLT rate of 30%. The maximum number of subjects evaluated for DLT for each dose level will be 12 subjects (about 4 cohorts of 3 subjects) if the dose escalation decision is to stay at the current dose from the first 3 cohorts. Based on the above design, the dose escalation decision rules for each dose level are:

- Dose escalate if the observed DLT rate <25%;

- Stay at the current dose if the observed DLT rate between 25%-33%;
- Dose de-escalate if the observed DLT rate >33%;

See Table 3 for dose escalation decision rules based on the total number of subjects evaluable for DLT and the number of subjects with DLT observed.

Table 3 SL-172154 Dose Escalation Decision Rules for Each Dose Level Based on mTPI-2

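### SAP 8.2 pools violating dose levels by a simple average of DLT rates, which equals isotonic regression only when the levels have equal numbers of evaluable subjects

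*SAP*

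**What the plan says.** - Protocol 9.2.4 names the method: "The MTD will be estimated using isotonic regression (based on the DLTs observed in DLT-evaluable subjects". It gives no pooling formula and no weights. The MTD is the dose whose isotonic estimate is nearest 30% among doses with an isotonic estimate of at least 25%. It adds: "A Maximum Administered Dose (MAD) will be reported if the isotonic estimate of DLT rate is less than 25% for all dose levels".
- SAP 3.2.1 describes an mTPI-2 design "with target DLT rate of 30% for the MTD", with cohorts of about 3, a minimum of 3 evaluable subjects before a decision, and at most 12 per level.
- SAP 8.2 explains pooling through an example in which the observed rates "at four dose levels are (0/3, 1/3, 0/3, 4/15". Levels 2 and 3 violate monotonicity: "the DLT estimates are replaced with their average", computed as (1/3+0/3)/2 = 1/6. Weighting by number of subjects is not mentioned.
- On the label, SAP 8.2 says: "A MAD will be reported if the DLT rate never reaches" 25%. It does not say whether that rate is observed or isotonic.
- Protocol 9.1.4, repeated in SAP 3.3, lets the sponsor depart from the planned numbers: in consultation with the safety committee it "may also elect to add subjects to the dose escalation cohorts if additional data is needed".
- SAP 11 declares no change from the protocol-specified analyses.

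**The concern.** Isotonic regression of proportions pools counts, so each level contributes in proportion to its evaluable subjects. The only pooling arithmetic in either document is an unweighted mean of rates, under which a level with 3 subjects counts as much as one with 12. Unequal numbers are normal in this design.

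The isotonic estimate is compared with the 25% cut and the 30% target, and the MTD or MAD is a primary outcome measure. A programmer who follows SAP 8.2 literally and one who runs a standard weighted routine could get different estimates from the same data.

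**Working it through.** **1. The SAP's own example.** Weighted: (1+0)/(3+3) = 1/6. Simple: (1/3+0/3)/2 = 1/6. Both give (0%, 16.7%, 16.7%, 26.7%) and Dose Level 4. The printed figure is correct, but only because both violating levels have n = 3.

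**2. The two formulas.** For violating levels with x1/n1 and x2/n2 DLTs:
- isotonic regression (pool-adjacent-violators): (x1+x2)/(n1+n2)
- SAP 8.2 read literally: (x1/n1 + x2/n2)/2

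For two violating levels, whose rates differ by definition, these agree only if n1 = n2.

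**3. Unequal n.** Results use the protocol's 25% rule and the tie rules. The higher level is taken to be the highest dose given, which is the MAD under Protocol 3.4.

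| Lower, higher level | Weighted | Simple average | Result, weighted | Result, simple |
|---|---|---|---|---|
| 3/3, 5/12 | 8/15 = 53.3% | (100%+41.7%)/2 = 70.8% | MTD, lower | MTD, lower |
| 4/12, 0/3 | 4/15 = 26.7% | (33.3%+0)/2 = 16.7% | MTD, higher | MAD, higher |
| 5/12, 0/3 | 5/15 = 33.3% | (41.7%+0)/2 = 20.8% | MTD, lower | MAD, higher |
| 3/6, 1/12 | 4/18 = 22.2% | (50%+8.3%)/2 = 29.2% | MAD, higher | MTD, higher |

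**4. The planned path.** Escalation needs a rate below 25% at the lower level, and stepping down needs a rate above 33% at the higher one. Two violating rates are therefore both below 25% or both above 33%, and any average stays on the same side of the cut. Listing every data state reachable under SAP Table 3 (three levels, start at 3.0 mg/kg, cohorts of 3, cap 12) confirms this:
- 2,029 states, of which 660 contain a violation
- the two estimates differ in 511 of the 660; the largest gap is 3/3 with 5/12, 70.8 − 53.3 = 17.5 points
- 0 changes of MTD/MAD label and 0 changes of selected dose

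These are counts of states, not probabilities. There are also no changes with cohorts of 3 or 4, or with Protocol Table 12.

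The zero for the dose uses the protocol's restriction of candidates to doses with an isotonic estimate of at least 25%. SAP 8.2 does not repeat it. Without it, a near-tie can move. Take 0/3, 6/9, 3/6: the upper two levels pool to 9/15 = 60%, which ties with 0% at 30 points from target, so the tie rule takes the lowest level. The simple average, (66.7%+50%)/2 = 58.3%, is nearer and selects the middle level, although 6/9 is already barred as unsafe in Table 3.

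**5. Off the planned path.** Suppose the lower level runs 1/3, 2/6 (stay), 2/9 (escalate), and the next level shows 0/3. If the sponsor adds 3 subjects at the lower level, 2 DLTs give 4/12 and 3 DLTs give 5/12: rows 2 and 3 of the table. Similarly, 0/3 below and 1/12 above, then 3 added below with 3 DLTs, gives row 4.

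**6. Direction.** Over all violating pairs with n of 3, 6, 9 or 12, reachable or not, the methods differ in 384 of 534. The simple average turns an MTD into a MAD in 6 and a MAD into an MTD in 15.

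**The case against.** The average appears inside an illustration. Both documents name the method as isotonic regression, and a statistician would use a weighted routine anyway. No figure in the SAP is wrong, and the planned rules never let the difference reach the label or, under the protocol's selection rule, the dose. The 17.5-point gap concerns two doses far above 30%. The recommended Phase 2 dose rests on the totality of the data, not on this estimate alone.

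Most of that stands, and it is why the point is minor. It does not remove the defect, because the illustration is the only operational instruction given and it does not generalise to the numbers this design produces.

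The label changes also depend on which 25% rule is read. If the SAP's rate is the observed one, 4/12 (33.3%), 5/12 (41.7%) and 3/6 (50%) each already call for an MTD, and the label changes in the table vanish. The dose change for 5/12 and 0/3 remains on that reading: a tie at 20.8% selects the higher dose under the SAP's tie rule, a tie at 33.3% the lower.

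A reader might infer more than the documents support:
- That the planned escalation could itself produce an MTD/MAD reversal. It cannot (step 4).
- That the error runs only from MTD to MAD. It runs both ways.
- That the pooled value is the DLT rate the trial will report. SAP 8.2 presents the observed number and percentage with DLT by dose level, and nothing says the isotonic estimate replaces them.

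**Conclusion.** The concern holds as a wrong pooling rule with limited consequences. Read literally, SAP 8.2 departs from the isotonic regression the protocol names whenever violating levels have unequal n, by up to 17.5 points on the planned path with cohorts of 3. There it never changes the MTD/MAD label, nor the selected dose under the protocol's candidate rule. Either can change only if the sponsor uses its discretion to add subjects at a lower level. Of the worked cases, 4/12 with 0/3 and 3/6 with 1/12 change the label but not the dose; 5/12 with 0/3 changes both.

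How often that would happen cannot be derived from the documents. A simulation that assumed five toxicity scenarios and a top-up of the lower level to 12 changed the MTD/MAD result in 0.4% to 1.8% of trials. The scenarios and the top-up size are assumptions, so the figure is only indicative. The label results also assume the protocol's isotonic reading of the 25% rule.

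**What to change.** In SAP 8.2:
- state that violating levels are pooled as total DLTs divided by total DLT-evaluable subjects (pool-adjacent-violators weighted by n);
- replace the example with one where the violating levels have unequal n;
- apply the 25% MAD rule to the isotonic estimate, as Protocol 9.2.4 does, and carry over its restriction of MTD candidates to doses with an isotonic estimate of at least 25%.

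The cost is a sentence or two and a new example. The design, the data collected and the dose-decision rules are unaffected.

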8.3 Adverse Events

Safety reporting of AEs commences when a subject has signed the ICF, throughout the course of treatment, and up to 30 days after the last dose of study drug. If another anti-cancer agent is started within 30 days after the last dose of study drug, only serious adverse events (SAEs) and AEs that occur prior to starting the new anti-cancer therapy should be recorded. After signing of informed consent, but prior to initiation of study drug, only AEs caused by a protocol-mandated procedure will be collected (e.g., AEs related to invasive procedures such as biopsies).

The AE terms on the eCRFs will be mapped to the preferred terms (PT) and system organ classes (SOC) using the Medical Dictionary for Regulatory Activities (MedDRA) in the most current version available at time of analysis. Drug-related AEs are defined as AEs with relationship to study treatment being related or possible related. A worst-case scenario approach will be taken to handle missing data, i.e. AEs with missing relationship to a study drug will be treated as drug-related AEs.

All AEs with onset dates on or after the first dose of study treatment are defined as treatment-emergent adverse events (TEAEs). Only TEAEs will be included in AE tables. All AEs will be

listed, and pretreatment AE, defined as AEs that start prior to the first date of the study treatment, will be flagged in relevant listings.

If both the start and end dates are completely missing, the AE will be considered treatment-emergent. Partial start and end dates may be imputed similarly as described for prior and concomitant medications in Section 6.8 for the purpose of determining treatment-emergent and AE duration.

An overview summary of TEAEs will be produced, including the counts and percentages of subjects with any TEAE, drug-related TEAEs (separate rows for SL-172154, PLD, and MIRV), serious TEAEs, drug-related serious TEAEs (separate rows for SL-172154, PLD, and MIRV), infusion related reaction AEs, Grade 3 or 4 AEs, drug-related Grade 3 or 4 AEs (separate rows for SL-172154, PLD, and MIRV), fatal TEAEs, and TEAEs leading to infusion interrupted, dose reduced, dose not given/delayed, and drug withdrawn.

The TEAE by maximum toxicity grade summary tables will use the following algorithms for counting subjects:

- **PT rows:** each subject is counted once within each unique PT at the maximum grade. For example, if a subject has two headaches, the subject is counted only once under the PT “Headache”. Subjects experiencing the same PT several times with different grades will only be counted once at the maximum grade.
- **SOC rows:** each subject is counted only once at the maximum grade at each SOC level although they may have several different PT events within the same SOC.
- **Any event row:** each subject with at least one TEAE will be counted only once at the maximum grade no matter how many events they have.

All TEAEs and drug-related TEAEs will be summarized by MedDRA SOC, PT and maximum toxicity grade. The SOC and PT will be ordered by descending order of the subject incidence of SOC and PT within each SOC based on all subjects in the analysis population.

The following summary tables will be presented by MedDRA PT, in which the PT will be order by descending order of subject incidence of PT based on all subjects in the analysis population:

- Summary of all TEAEs
- Summary of DLTs
- Summary of serious TEAEs
- Summary of drug-related TEAEs (separate tables for SL-172154, PLD, and MIRV)
- Summary of drug-related serious TEAEs (separate tables for SL-172154, PLD, and MIRV)
- Summary of fatal TEAEs
- Summary of Grade 3 or 4 TEAEs

- Summary of drug-related Grade 3 or 4 TEAEs (separate tables for SL-172154, PLD, and MIRV)
- Summary of TEAEs leading to infusion interrupted, dose reduced, dose not given/delayed, and drug withdrawn (separate tables for SL-172154, PLD, and MIRV)

Additional summaries for SL-172154-related IRR (toxicity grade, seriousness, number of events, action taken) at event-level, at subject-level, and number of subjects with IRR at each dosing visit among the first two cycles and during all subsequent cycles combined will be provided. For the MIRV cohort, MIRV-related Grade 3 or 4 ocular toxicity TEAEs, with SOC='Eye disorders', will be listed and summarized.

Listings of all AEs, drug-related AEs, DLTs, Grade 3 or 4 AEs, fatal AEs, and SAEs will be provided. Separate listings will be provided for AEs leading to infusion interruption, dose reduction, dose not given/delayed, and drug withdrawal with SL-172154, PLD, and MIRV, respectively. SL-172154-related IRR along with signs/symptoms, premedication and concomitant medication for IRR will also be listed. All AEs for the Screen Failures population will be presented in a listing as well.

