For all subjects in all cohorts, premedication as prophylaxis for IRR with dexamethasone (8 mg IV), an antipyretic and antihistamines should be administered at least 30 minutes prior to each SL-172154 administration. For dosage and schedule of prophylactic premedications, please see Section 5.1.1. For subjects enrolled to receive MIRV, premedication with an antipyretic, antihistamine, and dexamethasone will be administered at least 30 minutes prior to each MIRV administration as described in Section 5.3.2.1.

Throughout the treatment period for all subjects, an ongoing review of available safety data will be undertaken by a SMC as described in Section 7.8. All subjects (dose escalation and dose expansion) will receive SL-172154 administered with either PLD or MIRV until documented disease progression, unacceptable toxicity or intolerance, withdrawal of consent, or the subject meets other criteria for discontinuation (whichever occurs first) as defined in Section 3.1.1.

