16.8 Summary of Changes from Version 1.0 to 2.0

This amendment applies to all Investigator sites participating in this study. This amendment includes dexamethasone premedication prior to SL-172154 dosing, with revised guidelines for management of IRR despite premedication, and the addition of dose modifications in the context of Grade 2/3 liver enzyme elevations (the subject of SL03-OHD-105 Protocol Safety Update Memo dated 23-Oct-2023); and clarification of the method visual acuity assessment (the subject of SL03-OHD-105 Protocol Clarification Memo No. 4 dated 05-Dec-2023). Other revisions include updates to collection of samples for SL-172154 PK and ADA, and addition of C-reactive protein assessments at screening and to ad-hoc labs collected in the event of CRS or IRR AEs.

A summary of the changes to this protocol from Version 1.0 (dated 20-Jun-2023) are described in the table below:

Section	Description/Rationale
Throughout the protocol	Based on data from ongoing studies with SL-172154, dexamethasone 8 mg IV is added to prophylactic premedication prior to each dose of SL-172154. Subject of SL03-OHD-105 Protocol Memo dated 23-Oct-2023.
Section 3.6.1 Prohibited Medications or Treatments	Adjustments on use of steroids for IRR made based on dexamethasone use for premedication.
Section 3.7.1.1 Management of IRR [SL-172154]	Provided guidelines for Grade 2, recurrent Grade 2, Grade 3, and recurrent Grade 3 IRR following SL-172154 dosing if it occurs despite premedication with dexamethasone. Subject of SL03-OHD-105 Protocol Memo dated 23-Oct-2023.
Section 3.7.1.3 Management of Hepatotoxicity	Modifications to the guidance table for dose of SL-172154 in the context of Grade 2 or 3 liver enzyme elevations, based on emerging data from this study. Subject of SL03-OHD-105 Protocol Memo dated 23-Oct-2023.
Section 3.7.1.4 Management of Hematologic AEs	Addition of consult with Medical Monitor for management of Grade 4 hematologic AE in event of transient decrease in hemoglobin.
Section 3.7.3.2 Dose Modifications for MIRV-Related AEs	Modifications to the guidance table for dose of MIRV in the context of Grade 3 liver enzyme elevations, based on emerging data from this study. Subject of SL03-OHD-105 Protocol Memo dated 23-Oct-2023.

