16.9 Summary of Changes from Version 2.0 to 2.1

This is a country specific amendment for Spain and applies to Investigator sites participating in this study in Spain. At the AEMPS request, 16.8 Summary of Changes from Version 1.0 to 2.0 was revised to include detailed justification and reason for each of the changes. In addition, some of the text that was deleted due to an oversight in Section 3.7.1.1, Management of IRRs, was added back into Protocol Amendment version 2.1, and the text was revised as needed to reflect the updated IRR guidance.

A summary of the changes to this protocol from Version 2.0 (dated 29-Feb-2024) are described in the table below:

Section	Description/Rationale
Throughout the protocol	
Description of Change: Based on data from ongoing studies with SL-172154, dexamethasone 8 mg IV is added to prophylactic premedication prior to each dose of SL-172154. Subject of SL03-OHD-105 Protocol Memo dated 23-Oct-2023.
 
Rationale/Justification: Infusion-related reaction (IRR) is a common SL-172154-related treatment emergent AE. Addition of dexamethasone as primary prophylaxis to the standard premedication regimen of acetaminophen, H1 and H2 blockade was shown to be effective in reducing the incidence and severity of IRR symptoms in a parallel study (SL03-OHD-104). The data from SL03-OHD-104 study were shared with the safety monitoring committee for the SL03-OHD-105 study. The safety monitoring committee agreed to the addition of dexamethasone 8 mg IV to the premedication prior to each dose of SL-172154 in the current study.

Section 3.6.1 Prohibited Medications or Treatments	
Description of Change: Adjustments on use of steroids for IRR made based on dexamethasone use for premedication.
 
Rationale/Justification: Previous version of the protocol prohibited primary prophylactic use of steroids for the prevention of SL-172154 associated IRR. With the addition of dexamethasone to the premedication regimen prior to each SL-172154 infusion, the previous text was no longer applicable. Therefore, it was deleted, and clarification was added that steroid premedication prior to each SL-172154 administration for IRR prophylaxis is required.

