For all subjects in all cohorts, premedication as prophylaxis for infusion related reaction (IRR) with an antipyretic and antihistamines should be administered at least 30 minutes prior to each SL-172154 administration. For subjects enrolled to receive MIRV, premedication with an antipyretic, antihistamine, and dexamethasone will be administered approximately 30 minutes prior to each MIRV administration. Prophylactic use of eye drops with MIRV administration is also described in Section 5.3.2 of the protocol. Premedication (any agent except steroid) as prophylaxis for nausea and vomiting with PLD may be administered per institutional guidelines.

Further details of the study design and inclusion/exclusion criteria are described in Sections 3 and 4 of the protocol.

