6.7 Premedications

Premedications will be recorded on “Premedications” CRF page. Premedications will be coded to Anatomical Therapeutic Chemical (ATC) class and Generic Drug Names using the WHO Drug Dictionary and will be listed.

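### The SAP's infusion-related reaction tables pool SL-172154 infusions given before and after dexamethasone was added to premedication, so they give no rate for the current regimen

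*SAP*

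**What the plan says.** SAP 8.3 promises "Additional summaries for SL-172154-related IRR (toxicity grade, seriousness, number of events, action taken) at event-level, at subject-level". It adds that the "number of subjects with IRR at each dosing visit among the first two cycles and during all subsequent cycles combined will be provided". SAP 13.1 turns this into tables 14.3.1.20.1 to 14.3.1.22.1. Under SAP 5.2 the columns are dose level within escalation and expansion, then the same dose level with both phases combined, then all subjects on the regimen.

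Premedication enters the reporting only through listings. SAP 6.7 has it coded "using the WHO Drug Dictionary and will be listed", and SAP 8.3 says "SL-172154-related IRR along with signs/symptoms, premedication and concomitant medication for IRR will also be listed".

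On the premedication itself, SAP 3.1 says "premedication as prophylaxis for infusion related reaction (IRR) with an antipyretic and antihistamines should be administered", without dexamethasone. Protocol 3.1 says "premedication as prophylaxis for IRR with dexamethasone (8 mg IV), an antipyretic and antihistamines should be administered". The amendment history dates the change. Protocol 16.8 records that "dexamethasone 8 mg IV is added to prophylactic premedication prior to each dose of SL-172154" and points to a memo of 23-Oct-2023. Protocol 16.9 describes the rule before it: "Previous version of the protocol prohibited primary prophylactic use of steroids for the prevention of SL-172154 associated IRR".

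**The concern.** The sponsor changed IRR prophylaxis during the trial because the change was expected to alter how often IRR occurs and how severe it is. A table that counts infusions from both sides as one group describes neither rule. Safety and tolerability form a primary objective, and Protocol 16.9 calls IRR a common treatment-emergent event related to SL-172154. A reader of the study report will want to know how often IRR occurs with the premedication now in use, and the planned tables cannot answer that.

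Two features add to the difficulty. In a subject-level table, a subject treated across the change keeps an early reaction that occurred without dexamethasone. In the by-visit table, such a subject contributes early visits under one rule and later visits under the other, so a fall over visits could be read as growing tolerance when it may reflect premedication.

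**Working it through.** The point concerns what the tables contain, so most of the check is a comparison of text.

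1. **Did the rule change while subjects were on treatment?** Protocol v1.0 is dated 20 June 2023, the memo 23 October 2023 (125 days later) and v2.0 29 February 2024 (129 days after the memo). Protocol 16.9 says that the hepatotoxicity guidance in the same memo was based on data emerging from this study. Subjects had therefore been treated by then, presumably under the rule against primary steroid prophylaxis. Their number is not given.

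2. **Does the SAP cover both periods?** Yes. SAP 1 lists every protocol version from v0.0 to v3.0, and SAP 8 uses all treated subjects.

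3. **Does any planned table separate the periods?** No IRR table in SAP 8.3 or 13.1 has a premedication or period factor. The phase-specific columns might separate the periods by chance, but neither document says when expansion opened. The combined columns pool in any case.

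4. **Do the listings fill the gap?** Only in part. The IRR listing shows premedication for subjects who reacted, which gives numerators. The denominators, meaning infusions or subjects with and without dexamethasone, would have to be assembled by hand from the premedication and administration listings (16.2.4.7 and 16.2.5.1). In an abbreviated report, SAP 13.1 also drops the subject-level and by-visit tables (14.3.1.20.1 and 14.3.1.22.1) and keeps the pooled event-level table (14.3.1.21.1).

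5. **How large could the effect be?** The documents do not supply the inputs. By way of illustration only:
   - Let f be the share of subjects first treated without dexamethasone, p0 the IRR rate without it and p1 the rate with it.
   - Pooled rate = f × p0 + (1 − f) × p1. Excess over the with-dexamethasone rate = f × (p0 − p1).
   - p0 is borrowed from the monotherapy study in Protocol 1.7.1: 17/26 = 65.4%, which agrees with the figure printed there. p1 and f are assumed.

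| p1 (assumed) | Excess at f = 10% | f = 25% | f = 50% | f = 75% |
|---|---|---|---|---|
| 20% | 4.5 points | 11.3 | 22.7 | 34.0 |
| 35% | 3.0 | 7.6 | 15.2 | 22.8 |
| 50% | 1.5 | 3.8 | 7.7 | 11.5 |

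For example, with p1 = 35% and f = 50% the pooled rate is 0.5 × 65.4 + 0.5 × 35 = 50.2%, an excess of 15.2 points. The spread from 1.5 to 34.0 points shows how little can be said about size.

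**The case against.** The case for leaving the tables alone has several parts.

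- **The link is already reported.** Premedication is listed for each IRR, every listing is delivered even for an abbreviated report, and nothing is tested. This is true, but a listing gives no rate and no denominator.
- **The phase columns may already separate the periods.** If expansion opened near the memo date, they largely would. A reader might infer that escalation and expansion cut across the change. The documents do not show that; they show only that no alignment is stated.
- **The 65.4% anchor does not belong to this trial.** This stands. It comes from monotherapy at 0.1 to 10 mg/kg on other schedules, with 9 of 26 subjects at 0.1 or 0.3 mg/kg and infusions of 30, 60 or 120 minutes (Protocol 1.4.7). Protocol 1.7.1 says that IRR frequency rose with dose, and describes primary prophylactic premedication only for the 10 mg/kg group. In the present trial, dexamethasone was added to an existing antipyretic and antihistamine regimen, and infusions were lengthened. The table above cannot be read as an estimate.
- **Dose selection is not shown to be affected.** A reader might infer that the recommended Phase 2 dose rests on a misleading IRR rate. Protocol 3.4 bases that choice on the totality of safety, tolerability, PK, PD and efficacy data, and Protocol 16.9 records that the safety monitoring committee saw the parallel-study data and agreed to the change.
- **A simple yes/no split by infusion would itself mislead.** This also stands. It would mix first and later infusions. The old rule barred only primary prophylaxis, so some earlier infusions with dexamethasone might be in subjects who had already reacted. IRR management rules changed at the same time (Protocol 16.9), so the action-taken rows come from two sets of rules whatever dexamethasone does. These limits shape the fix; they do not remove the need for it.

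**Conclusion.** The point holds as a gap in description. IRR prophylaxis changed mid-study for a reason that bears directly on IRR, and the planned tables pool across the change in their combined columns. They will therefore not report an IRR rate under the current premedication. If the effect claimed from the parallel study carries over, the pooled rate would overstate IRR for that regimen. That direction is an assumption, and the size is unknown.

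The conclusion rests on the amendment history for timing and on the inference that SL-172154 infusions in this trial preceded the memo. It does not depend on the illustrative figures. It does not extend to saying that the phase columns fail to track the change, or that dose selection is distorted. It is a worthwhile, inexpensive improvement to make before database lock.

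**What to change.** In SAP 8.3, add to tables 14.3.1.20 to 14.3.1.22:

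1. **Main comparison, subject level:** subjects split by whether dexamethasone was recorded before their first SL-172154 dose.
2. **Supporting, infusion level:** IRR by whether dexamethasone was recorded before that infusion, shown by dosing visit, with the number of infusions given as the denominator.

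Derive both from the Premedications CRF page, not from calendar date. The protocol is not uniform on the status of the steroid (Protocol 1.7.1 calls premedication mandatory, 3.6.1 speaks of permission, and 5.1.1 lets the investigator modify it), so date is only a proxy. In the MIRV regimen the derivation must link the steroid to the SL-172154 infusion, because Protocol 5.3.2.1 has a separate dexamethasone premedication before MIRV.

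Label both splits as descriptive and non-randomised, state in a footnote that the IRR management rules changed at the same time, and flag subjects treated across the change.

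Separately, as an editorial matter, reconcile the SL-172154 premedication text in SAP 3.1 with Protocol 3.1.

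The cost is smaller groups per column and some added programming. No new data are needed.
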